7.1.1.11 Follow-up of Adverse Events

All AEs experienced by a subject, irrespective of the suspected causality, will be monitored until the event has resolved, any abnormal laboratory values have returned to baseline or stabilized at a level acceptable to the Investigator, Medical Monitor and/or the Sponsor, or until there is a satisfactory explanation for the changes observed, or until the subject is lost to follow-up.

7.1.1.12 Safety Reporting to Investigators, IECs, and Regulatory Authorities

The Sponsor will be responsible for reporting all SUSARs and any other applicable SAEs to regulatory authorities, Investigators and IECs, as applicable, in accordance with national or regional regulations in the countries where the study is conducted. Day zero is the first day of awareness of the event by the Sponsor or Sponsor's designee. SUSARs will be submitted within 7 days for fatal and life-threatening events and within 15 days for other SUSARs, unless otherwise required by national regulations. The Sponsor will also prepare an expedited report for Events Requiring Other Actions, where these might materially alter the current risk-benefit assessment of the study drug or that would be sufficient to consider changes in the study drug administration or in the overall conduct of the trial. The investigational site also will forward a copy of all expedited reports to his or her IECs in accordance with national regulations. In addition, once a year throughout the clinical trial or upon request, a Development Safety Update Report (DSUR) will be submitted to the concerned regulatory authority and IEC taking into account all new available safety information received during the reporting period.

7.1.2 Clinical Laboratory Safety Tests

Laboratory assessments will be performed by a central laboratory. Details of the urine and blood sampling procedures and any subject restrictions (e.g., withholding supplements) and subsequent storage and shipment of samples can be found in the REN001-202 Laboratory Manual. Sites will be provided with laboratory kits from the central laboratory. Details of parameters to be tested are listed in [Table 4](#). Approximate volume of blood to be taken from each subject during the study is detailed in [Table 5](#). Additional blood may be required for repeats of safety laboratory tests.

Table 4: Safety Laboratory Parameters

Biochemistry Albumin, Alanine aminotransferase (ALT), Aldolase Alkaline phosphatase (AP), Aspartate aminotransferase (AST) Bilirubin (Total, direct and indirect) Calcium, Cholesterol (Total, LDL and HDL), C-reactive protein Creatinine, Creatine Kinase (CK) eGFR using CKD-EPI Gamma glutamyl transferase (GGT), Glucose (non-fasted) Lipase Magnesium Phosphate, Potassium, Protein (Total) Sodium Triglycerides, Urea, Uric acid Bone and Calcium Markers Bone Specific alkaline phosphatase (BSAP) Parathyroid Hormone Vitamin D Endocrine and biomarker assays FSH (females ≥45 years not confirmed as post-menopausal, or if menopausal symptoms develop) Human chorionic gonadotropin (hCG) (WOCBP only) Troponin I
	
Haematology Basophils Eosinophils Haemoglobin Haematocrit (Packed cell volume) Large unstained cells Lymphocytes Mean corpuscular volume (MCV) Monocytes Neutrophils Platelet count Red cell count Reticulocytes White cell count HbA1c

Serological Markers HBsAg, HBcAb, Anti-hepatitis C virus serology (by multi-antigen enzyme immunoassay (EIA), HIV
	

Urinalysis -Blood, Glucose, Ketone, Protein, pH, Specific Gravity, Nitrite, Leukocytes, Bilirubin and Urobilinogen. Any significant abnormalities should be investigated via microscopy -Pregnancy Testing: hCG. Urine home pregnancy test kits will be supplied to allow monthly testing between study centre visits. -Testing for drugs of abuse: cocaine, cannabinoids, opiates, barbiturates, benzodiazepines, methadone, and amphetamines. Urine Biomarker assay -Urine N-terminal telopeptide (NTX).
	

Laboratory tests results can be repeated if necessary. Any clinically significant abnormal laboratory test result (e.g., findings that lead to more extensive investigation and/or indicate a risk to the health of the subject) should be reported as an AE. The Investigator should assess the possible relationship to study drug as is the case for all other AEs.

Table 5: Approximate Blood Volume Required for Study

Test	No. samples after baseline over 48 months ¹	Vol (ml)	Total (ml)
Haematology (including HbA1c) ²	10	2	20
Biochemistry (including aldolase, troponin I, FSH and hCG as applicable) ³	10	5	50
PK samples	14	4	56

¹Two additional samples needed for screening and baseline safety bloods if enrolment of mtDNA-PMM subjects is after participating in Study REN001-101 or after exiting STRIDE, and nDNA-PMM subjects (maximum of 14 ml extra taken over the screening and baseline period).

² There will be an additional 2 Haematology samples collected for German subjects (8 samples rather than 6), totaling 16ml

³ There will be an additional 2 Biochemistry samples collected for German subjects (8 samples rather than 6), totaling 40ml

Test	No. samples after baseline over 48 months ¹	Vol (ml)	Total (ml)
Bone and calcium markers (including BSAP, PTH, and vitamin D)	9	4	36
Total volume over study (mL)			162

7.1.3 Physical Examination (including weight and height)

All physical examinations will be carried out by a qualified person. Subjects enrolling at STRIDE Week 24 will have had a symptom-directed physical examination in STRIDE.

Subjects with mtDNA-PMM enrolling at STRIDE FU or from study REN001-101 (UK only), or after exiting STRIDE, and nDNA-PMM subjects will have a full physical examination at baseline, to include an assessment of head, neck, heart, lungs, abdomen, skin (including hair and nails), peripheral circulation, joints, general appearance, and a neurological examination.

Post baseline, subjects will have a brief symptom-directed physical examination, which should include general appearance, heart, lungs, skin, and a neurological examination. Clinically significant changes from the baseline examination should be assessed. Other systems examined should be determined by clinical findings and any AEs reported.

Height collected at screening/baseline visits only. Subjects should have weight and height measured while wearing indoor clothing and with shoes off.

7.1.4 Vital Signs

Blood pressure (systolic and diastolic mmHg) will be measured after subject has been supine for at least 5 minutes. The subject's dominant arm, where possible should be used throughout the study (and, where applicable, the same arm as used in the STRIDE study) and recorded to the nearest mmHg. Pulse (beats per minute) should be measured in the brachial/radial artery for at least 30 seconds. Body temperature will be recorded at all visits using a digital thermometer. Any results <35°C should be repeated to ensure correct placement of the thermometer.

7.1.5 Electrocardiogram (ECG) Recording

Single ECG measurements will be taken after the subject has rested for at least 10 minutes in a supine position using a 12-lead ECG machine.

To ensure safety of the subjects, a qualified individual at the site will evaluate all ECGs. If the QTcF is ≥ 500 msec for any post baseline ECG, the ECG intervals should be inspected carefully to ensure that the RR interval has been recorded correctly, and a single ECG will be repeated at 5-minute intervals 3 times. If these values are consistently high (>500 msec), as a precautionary measure, the subject will discontinue treatment. If a machine read QTcF value is prolonged, as defined above, repeat measurement may not be necessary, provided a qualified physician interpretation determines that the QTcF values are acceptable for the individual. In some cases, it may be necessary to repeat abnormal ECGs to rule out improper lead placement as contributing to the EC abnormality. ECGs may be sent to an ECG vendor for centralised reading at a later date if deemed necessary.

7.1.6 Eye Examination

All eye examinations should be carried out by an appropriately qualified professional. Best efforts should be made to ensure the same professional undertakes the slit lamp examinations for a particular subject in both the STRIDE study and in this long-term safety study. If the lens is clear, that should be recorded. If a cataract is identified, the cataract should be

classified and graded against the Lens Opacity Classification System III, ([Chylack et al, 1993](#)).

In addition, best corrected distance visual acuity (including refraction) should be assessed.

For scheduling reasons, the above assessments may be conducted \pm 14 days of the visit window given for the eye assessments.

In addition, any subject who experiences any visual symptoms during the study should have an additional eye examination as appropriate.

Eye examinations will not be repeated if within 6 months of a previous test within STRIDE.

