6 STUDY CONDUCT

Depending on IEC and regulatory approvals, this study may be conducted at a minimum of 30 study sites. Details of study assessments are provided in [Section 7](#).

Following baseline, visits should occur within the scheduled timeslot for the visit; see [Table 3](#), Schedule of Activities. Where possible, visits should occur on the target visit day in relation to the first day of study drug dosing.

Site staff will provide subjects with meals and snacks at appropriate times during the visit so that study drug is taken with food and to ensure subjects have enough energy prior to completing the exercise tests as required.

All PROs should, where possible, be completed prior to the 12MWT, and the 12MWT should be performed at least 2 hours after a snack. The 12MWT should be conducted at the same time of day on every occasion where possible.

Where a study centre requires, subjects may be asked to have a negative COVID-19 test prior to undertaking scheduled visits at the study centre.

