6.1.3.1 Screening Visit

- Obtain written informed consent. Subjects should be given adequate time to think about whether they want to participate and to ask questions. The Investigator (or an appropriate delegate at the site) will obtain written consent from each subject prior to commencing any specific study related activities or assessments.
- Subject Demography.
- Complete Medical History (including prescription and non-prescription drugs/treatment, non-drug treatments, topical products, vitamins and dietary supplements taken in the last 4 weeks, alcohol, drugs of abuse and tobacco use. (See [Table 1](#) for prohibited medication and washout times).
- Review of ongoing concomitant medications and non-drug treatments. If subject is on any prohibited medications ([Table 1](#)), a washout period will be required and the baseline visit should be scheduled after the washout period.
- Review of pre-treatment events ([Section 7.1.1.1](#)).
- Full physical examination (including weight and height).
- ECG.
- Vital signs (including temperature).
- Urinalysis and drugs of abuse testing.
- Blood samples for:
 - Haematology and biochemistry (including HbA1c, HIV/Hepatitis B/C serology)
 - Serum pregnancy test (WOCBP)
 - Serum FSH testing for all females (≥ 45 years) enrolling from Study REN001-101 (UK only) or not confirmed as post-menopausal in the STRIDE study
- Eye examination (may be completed between Screening and Baseline visits). Eye examinations will not be repeated if within 6 months of a previous test within STRIDE.
- Optional DXA Scan (in those countries and sites where this is permitted). It should be scheduled as close as possible to the baseline visit, however if this is not feasible, then it must be performed within the 4 weeks after the baseline visit. Subjects must be checked against the Additional Criteria for Sites with approvals for DXA Scans ([Section 4.4](#)). All WOCBP must have a negative pregnancy test prior to the scan. All female subjects will require an FSH test if not confirmed as post-menopausal on the STRIDE Study. A STRIDE subject will not have a baseline DXA in this study if they had a Week 24 DXA in the STRIDE study. Details of how the DXA scan will be performed can be found in the DXA Manual. DXA scans will not be repeated if within 6 months of a previous scan within STRIDE.

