1. REN001-201 W24

The majority of subjects enrolling in REN001-202 will enroll at REN001-201 Week 24. This will prevent an interruption in dosing and reduce the number of study visits and assessments for subjects.

The REN001-201 Week 24 visit will also be the REN001-202 Baseline visit; data in the REN001-201 database for this visit will be copied across programmatically to the REN001-202 database to avoid sites having to re-enter the data. Any data from REN001-201 database repeated in the REN001-202 database will be removed from the tables, listings and analysis datasets prior to reporting the combined data from the two studies. For example, any ongoing AEs or medications at the REN001-201 Week 24 visit will be copied across to the REN001-202 database, where they may be updated if there is any status change (e.g., end date being available); hence the latest information on these events recorded in REN001-202 database will be used for reporting.

Dosing in REN001-202 will start the day after the REN001-201 Week 24 visit. However, to allow for scheduling of eye examinations and DXA scans these REN001-201 Week 24 assessments can occur up to 14 and 28 days respectively, after the first dose of study drug in REN001-202.

The schematic below details how subjects transition between the 2 studies and the visit naming convention throughout the 2 studies:

REN001-201 Treatment Group	REN001-201							REN001-202						
		Sc	BL	W2	W4	W12	W18	W24 BL	M1	M3	M6	M12	M18	M24
REN001	REN001							REN001						
	Sc	BL	M0.5	M1	M3	M4.5	M6	M7	M9	M12	M18	M24	M30	M54
Placebo	Placebo							REN001						
	Sc	BL	M0.5	M1	M3	M4.5	M6 *BL	M7 *M1	M9 *M3	M12 *M6	M18 *M12	M24 *M18	M30 *M24	M54 *M48

Footnote: Sc=Screening; BL=Baseline; FU=Follow-up; W=Week; M=Month.

* Baseline visit and nominal visits from start of REN001 treatment.

In REN001-202 visits occur every 6 months between Month 24 and Month 48 (i.e., Months 30, 36 and 42). Where applicable, a final follow up telephone call will occur approximately 30 days after the last dose of study drug.

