2. REN001-201 FU

Subjects who enroll at the REN001-201 FU visit will have had an interruption in study drug from the time of the REN001-201 Week 24 visit to the time of the combined REN001-201 FU and REN001-202 Baseline visits. This gap in study treatment is expected to be approximately 4 weeks. For reporting purposes, the nominal study visits in REN001-202 will be considered as a continuation from REN001-201 Week 24.

The REN001-202 Baseline visit data will either be collected at the visit or come from the REN001-201 FU visit if the assessment is performed at the FU visit. The exception to this is the eye examinations and DXA scans which will be taken from REN001-201 Week 24 visit; however, to allow for scheduling of eye examinations and DXA scans these REN001-201 Week 24 assessments can occur after the first dose of study drug in REN001-202. As above for REN001-201 W24 rollover subjects, data in the REN001-201 database for the FU visit will be copied across programmatically to the REN001-202 database to avoid sites having to re-enter the data. Any data from REN001-201 database repeated in the REN001-202 database will be removed from the tables, listings and analysis datasets prior to reporting the combined data from the two studies. For example, any ongoing AEs or medications at the REN001-201 FU visit will be copied across to the REN001-202 database, where they may be updated if there is any status change (e.g., end date being available); hence the latest information on these events recorded in the REN001-202 database will be used for reporting.

Dosing in REN001-202 will start on the day of the REN001-202 Baseline visit.

The schematic below details how subjects transition between the 2 studies and the visit naming convention throughout the 2 studies:

REN001-201 Treatment Group	REN001-201								REN001-202						
		Sc	BL	W2	W4	W12	W18	W24	FU BL	M1	M3	M6	M12	M18	M24
REN001	REN001								REN001						
	Sc	BL	M0.5	M1	M3	M4.5	M6		M7	M9	M12	M18	M24	M30	M54
Placebo	Placebo								REN001						
	Sc	BL	M0.5	W4	W12	W18	W24 *BL	→	M7 *M1	M9 *M3	M12 *M6	M18 *M12	M24 *M18	M30 *M24	M54 *M48

Footnote: Sc=Screening; BL=Baseline; FU=Follow-up; W=Week; M=Month.

* Baseline visit and nominal visits from start of REN001 treatment.

In REN001-202 visits occur every 6 months between Month 24 and Month 48 (i.e., Months 30, 36 and 42). Where applicable, a final follow up telephone call will occur approximately 30 days after the last dose of study drug.

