3. (a) REN001-201 Exit

Enrolment after exiting REN001-201 will result in a break in study participation of variable duration where the subject is off study drug and not monitored in either study. Due to the gap in monitoring and dosing, for reporting purposes, the subject's two participations will be considered as two separate subjects and data in REN001-202 will not be considered as a continuation from REN001-201.

These subjects will need to complete Screening and Baseline visits in REN001-202 to check eligibility prior to enrolment. If the subject had a DXA scan in REN001-201, then the REN001-201 Week 24 visit can be used as the Baseline assessment if there is 6 months or less since the assessment. Similarly, the REN001-201 Week 24 eye examination can be used as the Baseline assessment if there is a gap of 6 months or less.

Dosing in REN001-202 will start on the day of the REN001-202 Baseline visit.

The schematic below details how subjects transition between the 2 studies:

REN001-201 Treatment Group	REN001-201								Break in study participation	REN001-202							
	Sc	BL	W2	W4	W12	W18	W24	FU		Sc	BL	M1	M3	M6	M12	M18	M24
REN001	REN001									REN001 [^]							
	Sc	BL	M0.5	M1	M3	M4.5	M6	FU		Sc	BL	M1	M3	M6	M12	M18	M24
Placebo	Placebo									REN001							
	Sc	BL	M0.5	W4	W12	W18	W24	FU		Sc	BL	M1	M3	M6	M12	M18	M24

Footnote: Sc=Screening; BL=Baseline; FU=Follow-up; W=Week; M=Month.

[^] Data from REN001-202 will not be considered a continuation of REN001-201 but will be reported as a separate subject. In REN001-202 visits occur every 6 months between Month 24 and Month 48 (i.e., Months 30, 36 and 42). Where applicable, a final follow up telephone call will occur approximately 30 days after the last dose of study drug.

3. (b) REN001-101

REN001-101 completed in March 2020 and therefore subjects will not have received mavodelpar for more than 2 years at the time of entry to REN001-202. For reporting purposes, only data from the start of REN001-202 will be considered.

Subjects will need to perform Screening and Baseline visits in REN001-202 to check eligibility prior to enrolment.

Dosing in REN001-202 will start on the day of the REN001-202 Baseline visit.

The schematic below details the subject visits:

REN001-201 Treatment Group	REN001-201								REN001-202							
	Sc	BL	W2	W4	W12	W18	W24	FU	Sc	BL	M1	M3	M6	M12	M18	M24
NA	Not Applicable								REN001							
									Sc	BL	M1	M3	M6	M12	M18	M24

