6.7. EYE EXAMINATIONS

Eye examination data will be performed during the study by an appropriately qualified professional. Any abnormality considered clinically significant, will be reported as an AE.

To allow for scheduling of the eye examinations the REN001-201 Week 24 (Month 6) assessment can occur up to 14 days after the visit. Hence, this examination could occur after the start of administration of mavodelpar in REN001-202; this period is not considered sufficient time to have an impact on eye examination results. Therefore, for those mtDNA-PMM subjects who received placebo in REN001-201, enrolled in REN001-202 at REN001-201 Exit, enrol from study REN001-101 or for nDNA-PMM subjects this record will still be considered the baseline record relative to the start of mavodelpar provided it occurs within 14 days of the first dose of mavodelpar.

Baseline eye examinations will not be required for REN001-201 Exit subjects if the screening visit is within 6 months of the last REN001-201 examination.

Best corrected visual acuity (BCVA) can be assessed using the LogMAR scale, ETDRS letters or Snellen line. All results will be converted to the LogMAR scale before calculating changes from baseline at each visit for left and right eye BCVA (Roy 2003).

Where the Snellen scale has data recorded as x/y the MAR value is calculated by dividing y by x and then the LogMAR is the base 10 logarithm of the MAR value [i.e., $\text{LogMAR} = \log_{10}(\text{MAR})$]. Hence, higher scores indicate worse BCVA and increases from baseline indicate deterioration.

A change of 0.02 in LogMAR is equivalent to 1 letter. Hence, a Snellen scores with ‘-z’ or ‘+z’ indicating z letters fewer, or z letters more, respectively, will require an adjustment to the LogMAR score; 0.02 will be added or subtracted, respectively, for each letter (z).

e.g.,

$$20/15-1: \text{LogMAR} = \text{Log}_{10}(15 \text{ divided by } 20) + 0.02 = -0.105$$

$$20/15+1: \text{LogMAR} = \text{Log}_{10}(15 \text{ divided by } 20) - 0.02 = -0.145$$

If the Snellen scale is not reported in x/y format or x/y±z format, then the conversion to logMAR will not be done.

A change of 0.3 LogMAR (equivalent to 15 letters or 3-line change) is considered meaningful.

Refraction error based on spherical equivalent will be derived for each eye using the following formula:

$$\text{Spherical Equivalent (diopters)} = \text{cylinder (diopters)}/2 + \text{sphere (diopters)}$$

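### Protocol 7.1.6 repeats the six-month eye-examination waiver without its scope and, read literally, cancels the Month 3 examination for STRIDE Week 24 and follow-up enrollers

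*Protocol*

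**What the plan says.** Protocol 7.1.6, the general methods section for eye examinations, ends with "Eye examinations will not be repeated if within 6 months of a previous test within STRIDE". It sets no limit on visit or enrolment route. Section 6 tells sites "Details of study assessments are provided in" Section 7.

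Three other places carry the same rule with a scope:

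- Protocol 6.1.3.1 attaches it to the screening eye examination of Option 3 subjects (from REN001-101 or after exiting STRIDE): "may be completed between Screening and Baseline visits). Eye examinations will not be repeated if within 6 months of a previous test within STRIDE".
- SAP 3.8, pathway 3(a), on subjects who enrol after exiting STRIDE: "Similarly, the REN001-201 Week 24 eye examination can be used as the Baseline assessment if there is a gap of 6 months or less".
- SAP 6.7: "Baseline eye examinations will not be required for REN001-201 Exit subjects if the screening visit is within 6 months of the last REN001-201 examination".

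Protocol 6.3 lists an eye examination at Month 3 (Day 84) for all subjects without exception. Table 3 marks it at that visit, with no waiver footnote on the row. Under 6.1.1 and 6.1.2, Option 1 (Week 24) and Option 2 (follow-up visit) enrollers take their baseline eye examination from STRIDE Week 24.

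**The concern.** For Option 1 and Option 2 subjects the Week 24 test is a previous test within STRIDE, and Month 3 comes soon after it. A site that applies the closing line of 7.1.6 as written would omit the Month 3 examination; a site that follows 6.3 and Table 3 would perform it. The wording also reaches an early-withdrawal eye examination (6.9) done within six months of the STRIDE test.

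Formation or exacerbation of cataracts is one of three adverse events of special interest (7.1.1.5), and the number of such events is a primary endpoint (3.2.1). Month 3 is the first scheduled lens check on drug for subjects who switch from placebo. Most STRIDE subjects are expected to enrol at Week 24, so the conflict sits on the main enrolment route. What is at stake is uneven ascertainment between sites.

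**Working it through.** The plan gives no figure to reproduce. The check is date arithmetic.

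**Inputs**

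- W is the STRIDE Week 24 visit date. The last STRIDE dose is assumed to fall on W.
- Option 1: first dose the day after Week 24 (SAP 3.8), so Day 1 = W+1.
- Option 2: Day 1 is the follow-up visit, 21 to 28 days after the last dose (SAP Appendix 2), so Day 1 = W+21 to W+28.
- Month 3 is Day 84, with a visit window of ±7 days (Table 3) and an eye window of ±14 days (6.3, 7.1.6). Together these give Day 63 to Day 105.
- The Week 24 test may be late: "assessment can occur up to 14 days after the visit" (SAP 6.7). SAP 3.8 counts the 14 days from the first dose instead: "these REN001-201 Week 24 assessments can occur up to 14 and 28 days respectively, after the first dose of study drug in REN001-202". For Option 1 that allows one more day and only shortens the gap. Up to 14 days early is an assumption that mirrors the ±14 days in 7.1.6.
- Six months is 6 × 28 = 168 days in study months (SAP 9.5 counts three months as 84 days), or 181 to 184 calendar days.

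**Formula.** Days from W to Day N = (N − 1) + days from W to Day 1.

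**Month 3, days after the Week 24 test**

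| | On target | With visit and eye windows | Also test 14 days late to 14 days early |
|---|---|---|---|
| Option 1 | 83 + 1 = 84 | 63 to 105 | 63 − 14 = 49 to 105 + 14 = 119 |
| Option 2 | 83 + 21 = 104 to 83 + 28 = 111 | 83 to 132 | 83 − 14 = 69 to 132 + 14 = 146 |

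Every value is below 168 and below 181. The Option 2 lower bound of 69 is not a true minimum, because SAP 3.8 says of follow-up enrollers that "these REN001-201 Week 24 assessments can occur after the first dose of study drug in REN001-202". A later test shortens the gap further and strengthens the result.

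**What it would take to escape the waiver.** Against the shorter threshold of 168 days, the Week 24 test would have to precede the Week 24 visit by more than 168 − 105 = 63 days (Option 1) or 168 − 132 = 36 days (Option 2).

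**Month 6.** On target the gap is 167 + 1 = 168 days for Option 1, or 168 − 14 = 154 if the Week 24 test was 14 days late. For Option 2 it is 167 + 21 = 188 to 167 + 28 = 195 days, or 174 to 181 with a late test. Whether Month 6 is caught depends on the definition of a month and the actual dates. The point does not rest on it.

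**Delay.** If Month 3 is skipped and Month 6 is done, a placebo switcher's first scheduled on-drug lens check moves from Day 84 to Day 168, which is 84 days later.

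**The case against.** The strongest reply is that no careful site would read 7.1.6 this way.

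- Section 7 describes how assessments are done. The visit sections and Table 3 say when, and 6.3 gives a specific order without exception.
- The sentence just before the waiver calls for an extra examination when visual symptoms occur. A fully literal waiver would cancel that too, so the natural meaning of repeating is repeating the entry examination.
- 7.1.7 carries a parallel DXA sentence, which suggests text copied from the Option 3 screening visit.
- A literal reading would empty the Month 3 eye examination for most mtDNA subjects, which plainly cannot be intended.
- Nothing in the documents shows that any site skipped an examination, and no endpoint, baseline or analysis definition changes.

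Most of this stands as evidence of intent and as a limit on severity. Later scheduled examinations continue. The cataract signal came from one high-dose six-month rat study and did not appear in the three-month rat or twelve-month primate studies (1.4.2.2). None of it removes the contradiction. The limiting words are absent from 7.1.6, and two of the three places that supply them are in the SAP, which is not the site's operating instruction. Section 9.9 asks sites to follow the protocol exactly, and 6.3 and the literal 7.1.6 cannot both be followed.

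**Conclusion.** The concern holds. The closing sentence of 7.1.6 is an internal inconsistency: it drops the scope given in 6.1.3.1 and SAP 3.8 and 6.7, and as written it contradicts the Month 3 examination for every Option 1 and Option 2 subject under the windows above. The largest gap is 146 days against a threshold of at least 168. The result assumes that the last STRIDE dose was on the Week 24 visit date and that the Week 24 test was no more than 14 days early; the escape margins of 63 and 36 days show that it is not sensitive to the second assumption.

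This is a wording error in one operational sentence. It does not show a planned omission of lens checks. The consequence is a risk of inconsistent application between sites, with a possible 84-day delay in the first scheduled on-drug lens check for placebo switchers. It should be corrected, but it does not threaten the study.

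**What to change.** In 7.1.6, state that the waiver applies only to the REN001-202 screening/baseline eye examination of subjects enrolling after exiting STRIDE. Add that all scheduled post-baseline, early-withdrawal and symptom-prompted eye examinations are done whatever the date of the last STRIDE test.

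The cost is a short wording change that uses scope the sponsor has already written in 6.1.3.1 and the SAP. It brings 7.1.6 into line with 6.3 and Table 3 and adds no examination beyond those the protocol already calls for. The SAP needs no change.
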